4.2 Duration of Subject Participation and Study

Each eligible subject's participation includes a Screening Phase (within a maximum of 10 calendar days), Run-in Phase (single-blinded, up to 12 weeks) followed by the Treatment Phase (double-blinded, variable per subject). Study duration for individual subjects will vary, depending on their individual enrollment date. The common EoS will occur when 820 subjects have completed the Week 6 visit. Recruitment will be stopped when it is projected that a sufficient number of subjects have been enrolled in order for 820 subjects to reach the Week 6 visit. Sites will be notified of the common EoS date prior to study closure and should advise ongoing study subjects of the study termination date thereafter; see Section 8.4 for detailed description of the EoS procedures.

Patients who prematurely discontinue patiromer/placebo will remain in the study for the collection of composite endpoint event data up to and including the common EoS and will receive usual care during the study phase.

5. SELECTION AND WITHDRAWAL OF SUBJECTS

5.1 Number of Subjects

For detailed justification of the sample size please refer to Section 12.2.

5.2 Inclusion Criteria

The following criteria must be met for each subject prior to entry in the Run-in Phase:

1. Subject provides written informed consent prior to study participation
2. Age at least 18 years or greater
3. Current NYHA Class II–IV
4. Left ventricular ejection fraction $\leq 40\%$, measured by any echocardiographic, radionuclide, MRI, angiographic, or computerized tomography method in the last 12 months (without subsequent measured ejection fraction $>40\%$ during this interval)
5. Receiving any dose of a beta-blocker for the treatment of HF or unable to tolerate beta-blockers (reason documented)
6. eGFR ≥ 30 mL/min/1.73 m² at Screening (based on a single local laboratory analysis of serum creatinine and calculation using the CKD-EPI equation; see Section 9.2)
7. Hyperkalemia at Screening (defined by 2 local serum K⁺ values of >5.0 mEq/L, each obtained from a separate venipuncture, e.g., one in each arm or two separate venipunctures in the same arm) while receiving an ACEi/ARB/ARNi, and/or an MRA

OR

- Normokalemia at Screening (defined by 2 local serum K⁺ ≥ 4.0 – ≤ 5.0 mEq/L, each obtained from a separate venipuncture, e.g., one in each arm or two separate venipunctures in the same arm) with a history of hyperkalemia documented by a usual care serum K⁺ measurement >5.0 mEq/L while on RAASi treatment in the 12 months prior to Screening leading to a subsequent and permanent dose decrease or discontinuation of one or more RAASi medications
8. Females of child-bearing potential must be non-lactating, must have a negative pregnancy test at Screening, and must agree to continue using contraception (see Section 9.8) throughout the study and for 4 weeks after study completion

9. With hospitalization for HF or equivalent (e.g., emergency room or outpatient visit for worsening HF during which the patient received intravenous medications for the treatment of HF) within the last 12 months before Screening

- a) Without atrial fibrillation at Screening, BNP level must be greater than 150 pg/mL (18 pmol/L) or NT-proBNP must be greater than 600 pg/mL (71 pmol/L)
- b) With atrial fibrillation at Screening, BNP level must be greater than 300 pg/mL (35 pmol/L) or NT-proBNP must be greater than 1,200 pg/mL (142 pmol/L)

OR

Without hospitalization for HF or equivalent (e.g., emergency room or outpatient visit for worsening HF during which the subject received intravenous medications for the treatment of HF) within the last 12 months before Screening

- a) Without atrial fibrillation at Screening, BNP level must be greater than 300 pg/mL (35 pmol/L) or NT-proBNP must be greater than 1,200 pg/mL (142 pmol/L)
- b) With atrial fibrillation at Screening, BNP level must be greater than 600 pg/mL (71 pmol/L) or NT-proBNP must be greater than 2,400 pg/mL (284 pmol/L)

Note: Table 2 provides the same information of Inclusion Criterion 9 as described in the text above.

Table 2 BNP and NT-proBNP Threshold Levels (Based on Local Laboratory), Comorbidities, and Previous Hospitalizations

	Subjects with hospitalization for HF or equivalent ⁽¹⁾ within last 12 months	Subjects with no hospitalization for HF or equivalent ⁽¹⁾ within last 12 months
Subjects presenting without atrial fibrillation when the blood sample was collected	BNP ⁽²⁾ >150 pg/mL (18 pmol/L) or NT-proBNP >600 pg/mL (71 pmol/L)	BNP ⁽²⁾ >300 pg/mL (35 pmol/L) or NT-proBNP >1,200 pg/mL (142 pmol/L)
Subjects presenting with atrial fibrillation when the blood sample was collected	BNP ⁽²⁾ >300 pg/mL (35 pmol/L) or NT-proBNP >1,200 pg/mL (142 pmol/L)	BNP ⁽²⁾ >600 pg/mL (71 pmol/L) or NT-proBNP >2,400 pg/mL (284 pmol/L)

1 E.g., urgent emergency room or outpatient visit for worsening HF during which the subject received intravenous medications for the treatment of HF.

2 For subjects treated with ARNi (sacubitril/valsartan) in the previous 4 weeks before Screening only NT-proBNP values are to be considered.

Notes: ARNi=Angiotensin receptor/neprilysin inhibitor; BNP=Brain natriuretic peptide; HF=Heart failure; NT-proBNP=N-terminal pro b-type brain natriuretic peptide.

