Without hospitalization for HF or equivalent (e.g., emergency room or outpatient visit for worsening HF during which the subject received intravenous medications for the treatment of HF) within the last 12 months before Screening.

a) Without atrial fibrillation at Screening, BNP* level must be greater than 300 pg/mL (35 pmol/L) or NT-proBNP must be greater than 1,200 pg/mL (142 pmol/L).

b) With atrial fibrillation at Screening, BNP* level must be greater than 600 pg/mL (71 pmol/L) or NT-proBNP must be greater than 2,400 pg/mL (284 pmol/L).

*For subjects treated with ARNi (sacubitril/valsartan) in the previous 4 weeks before Screening, only NT-proBNP values are to be considered.

Note: The following table provides the same information of Inclusion Criterion 9 as described above.

BNP and NT-proBNP Threshold Levels (Based on Local Laboratory), Comorbidities, and Previous Hospitalizations		
	Subjects with hospitalization for HF or equivalent⁽¹⁾ within last 12 months	Subjects with no hospitalization for HF or equivalent⁽¹⁾ within last 12 months
Subjects presenting without atrial fibrillation when the blood sample was collected	BNP ⁽²⁾ >150 pg/mL (18 pmol/L) or NT-proBNP >600 pg/mL (71 pmol/L)	BNP ⁽²⁾ >300 pg/mL (35 pmol/L) or NT-proBNP >1,200 pg/mL (142 pmol/L)
Subjects presenting with atrial fibrillation when the blood sample was collected	BNP ⁽²⁾ >300 pg/mL (35 pmol/L) or NT-proBNP >1,200 pg/mL (142 pmol/L)	BNP ⁽²⁾ >600 pg/mL (71 pmol/L) or NT-proBNP >2,400 pg/mL (284 pmol/L)

1 E.g., emergency room or outpatient visit for worsening HF during which the subject received intravenous medications for the treatment of HF.

2 For subjects treated with ARNi (sacubitril/valsartan) in the previous 4 weeks before Screening only NT-proBNP values are to be considered.

Notes: ARNi=Angiotensin receptor/neprilysin inhibitor; BNP=Brain natriuretic peptide; HF=Heart failure; NT-proBNP=N-terminal pro b-type brain natriuretic peptide.

Exclusion Criteria:

Subjects who meet any of the following criteria during Screening will be excluded:

1. Current acute decompensated HF within 4 weeks before Screening. Subjects with a discharge from a hospitalization for acute decompensation of HF longer than 4 weeks before Screening may be included.
2. Symptomatic hypotension or systolic blood pressure <90 mmHg.
3. Significant primary aortic or mitral valvular heart disease (except secondary mitral regurgitation due to left ventricular dilatation).

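### Inclusion Criterion 9 converts BNP and NT-proBNP to pmol/L with one shared divisor, so the BNP limits in pg/mL and in pmol/L contradict each other

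*Protocol*

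**What the plan says.** Criterion 9 sets a natriuretic peptide limit in four cells: with or without a heart failure hospitalization (or equivalent) in the past 12 months, crossed with presence or absence of atrial fibrillation. Two of the cells have the same limits. A subject qualifies on BNP or on NT-proBNP. From the lowest limit to the highest, Protocol Section 5.2 states:

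- "BNP level must be greater than 150 pg/mL (18 pmol/L) or NT-proBNP must be greater than 600 pg/mL (71 pmol/L"
- "BNP level must be greater than 300 pg/mL (35 pmol/L) or NT-proBNP must be greater than 1,200 pg/mL (142 pmol/L"
- "BNP level must be greater than 600 pg/mL (71 pmol/L) or NT-proBNP must be greater than 2,400 pg/mL (284 pmol/L"

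The same figures stand in the Synopsis text ("BNP* level must be greater than 600 pg/mL (71 pmol/L) or NT-proBNP must be greater than 2,400 pg/mL (284 pmol/L"), in the Synopsis table and in Table 2.

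The title of Table 2, "BNP and NT-proBNP Threshold Levels (Based on Local Laboratory), Comorbidities, and Previous Hospitalizations", shows that local laboratory values decide. A footnote to that table narrows the use of BNP: "For subjects treated with ARNi (sacubitril/valsartan) in the previous 4 weeks before Screening only NT-proBNP values are to be considered". Neither document says which unit governs when the two disagree.

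**The concern.** The middle and outer limits put the same mass concentration, 600 pg/mL, beside the same molar concentration, 71 pmol/L, for both markers. BNP and NT-proBNP are different molecules; the protocol itself gives them separate limits and treats them differently in recent ARNi users. If their masses differ, at least one of the two conversions is wrong.

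This matters because the figures are an operative entry threshold applied by local laboratories in a multinational trial of approximately 375 sites. Where the two units disagree, whether a subject qualifies on BNP depends on the unit in which the laboratory happens to report. Risk at entry is most relevant to the CV death and CV hospitalization components of key secondary endpoints 4 and 5.

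**Working it through.** **Formula.** Because pg/mL equals ng/L, pmol/L = (pg/mL) ÷ (molar mass in kDa). The ratio of the two printed figures is therefore the molar mass that the protocol implicitly used.

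**Step 1: recover the divisor from the printed pairs** (Section 5.2 and Table 2).

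| Marker | pg/mL | pmol/L | Divisor | Range allowing for rounding of pmol/L |
|---|---|---|---|---|
| BNP | 150 | 18 | 8.33 | 8.11-8.57 |
| BNP | 300 | 35 | 8.57 | 8.45-8.70 |
| BNP | 600 | 71 | 8.45 | 8.39-8.51 |
| NT-proBNP | 600 | 71 | 8.45 | 8.39-8.51 |
| NT-proBNP | 1,200 | 142 | 8.45 | 8.42-8.48 |
| NT-proBNP | 2,400 | 284 | 8.45 | 8.44-8.47 |

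**Step 2: reproduce the protocol's figures with one divisor.** Dividing by 8.457 gives 17.7, 35.5 (35.47 before rounding) and 70.9 for BNP, and 70.9, 141.9 and 283.8 for NT-proBNP. To whole numbers these are 18, 35, 71 and 71, 142, 284, exactly as printed. The small spread in the BNP divisors is rounding only. The documents' own figures thus establish that one factor was applied to two peptides. They do not by themselves show which column is wrong.

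**Step 3: decide which column is wrong.** This needs molar masses that the documents do not give. Assumptions: BNP (32 residues) 3.4-3.7 kDa, with 3.464 kDa from summing the residues; NT-proBNP (76 residues) about 8.5 kDa, with 8.457 kDa from the same sum. The shared divisor then fits NT-proBNP, and the BNP column is in error.

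| BNP limit, pg/mL | Printed pmol/L | Recomputed pmol/L at 3.4-3.7 kDa | Printed pmol/L expressed in pg/mL | Share of pg/mL limit |
|---|---|---|---|---|
| 150 | 18 | 41-44 | 61-67 | 41-44% |
| 300 | 35 | 81-88 | 119-130 | 40-43% |
| 600 | 71 | 162-176 | 241-263 | 40-44% |

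For example, 600 ÷ 3.7 = 162 and 600 ÷ 3.4 = 176; 71 × 3.4 = 241 and 71 × 3.7 = 263; 241 ÷ 600 = 40% and 263 ÷ 600 = 44%. At 3.464 kDa the three shares are 41.6%, 40.4% and 41.0%.

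**Step 4: size relative to the criterion's own steps.** Under the same assumption, the printed 71 pmol/L (241-263 pg/mL) lies below the 300 pg/mL limit of the next step down, and the printed 35 pmol/L (119-130 pg/mL) lies below the lowest limit of 150 pg/mL. The printed pmol/L rule is looser by more than one step of the criterion.

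**Step 5: who could be affected.** All of the following must hold: the local laboratory reports BNP in pmol/L; the subject is assessed on BNP and was not on ARNi in the 4 weeks before Screening; no NT-proBNP value qualifies; and BNP lies between the printed and the recomputed pmol/L limit (for the highest limit, between 71 and about 162-176 pmol/L). The documents do not allow this group to be counted.

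**The case against.** The strongest case on the other side accepts the shared divisor and disputes its consequence.

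- **No shown effect on enrolment.** Neither document says that any local laboratory reports BNP in pmol/L, and pg/mL is printed first everywhere. A reader might infer that sites did enrol at about 41% of the limit, or that the population differs between countries. The documents do not support that; the effect is conditional and may be nil. This stands.
- **The percentage rests on outside constants.** True. The contradiction needs only that the two masses differ, but its direction and size need the assumed masses. The result moves little over the range tried.
- **No bias in the results.** A reader might infer that looser entry distorts the treatment comparison. It does not: allocation is 1:1 within geographic region, region is in the primary model, the primary endpoint is change in serum potassium, and the sample size assumptions (Protocol Section 12.2, SAP Section 1.5) do not involve BNP. Any dilution of risk would touch only the CV components of key secondary endpoints 4 and 5, the last two in the fixed sequence, and cannot be quantified. This stands.
- **Severity can be described another way.** Screening natriuretic peptide also goes to the central laboratory once the other criteria are met, and the SAP's NT-proBNP subgroups take the central screening value first (SAP Section 2.12.2). That helps to describe who was randomized, but neither document applies the central value to Criterion 9.
- **Timing.** Protocol Version 4.0 is dated 23 June 2021, and sites were told on 24 June 2021 that the study was closing (SAP Section 2.2). A letter to sites would change almost no enrolment. This stands.
- **Not deviations.** It is tempting to class anyone admitted below a corrected limit as an eligibility deviation. A subject above 18, 35 or 71 pmol/L met the criterion as printed, and may also have qualified on NT-proBNP. This stands.

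**Conclusion.** The inconsistency is real and concerns an operative eligibility threshold in four places: one divisor of about 8.45 was applied to two different peptides. That much follows from the printed figures, given that the two masses differ. On the assumed masses, the NT-proBNP equivalents are right and the BNP equivalents are too low, at about 40-44% of the stated pg/mL limits.

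The practical effect is conditional on pmol/L reporting of BNP, which the documents neither show nor exclude, and is limited to the narrow group in Step 5. The primary analysis, the randomized comparison, the sample size and the type I error are unaffected. The correction is worth making because it is cheap and because it determines how the entry criterion can be reported accurately.

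**What to change.** 1. The sponsor should confirm that pg/mL was the intended unit. Then, in the Synopsis text, the Synopsis table, Section 5.2 and Table 2, either recompute the three BNP pmol/L equivalents from the BNP molar mass, stating the mass used, or delete them and state that pg/mL governs.
2. Query the unit of every local BNP result used for Criterion 9.
3. List descriptively any randomized subject who qualified only on a BNP value in pmol/L below the corrected figure and had no qualifying NT-proBNP. Keep this listing apart from the protocol deviation summary in SAP Section 2.4. Central screening NT-proBNP can be shown beside it for context.

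The cost is three figures changed in four places, one data query and one short listing. No analysis set changes: the full analysis set requires only randomization and at least one dose of randomized treatment.

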5.3 Exclusion Criteria

Subjects who meet any of the following criteria during Screening will be excluded:

1. Current acute decompensated HF within 4 weeks before Screening. Subjects with a discharge from a hospitalization for acute decompensation of HF longer than 4 weeks before Screening may be included
2. Symptomatic hypotension or systolic blood pressure <90 mmHg
3. Significant primary aortic or mitral valvular heart disease unrelated to HF (except secondary mitral regurgitation due to left ventricular dilatation)
4. Heart transplantation or planned heart transplantation (i.e., currently on a heart transplant waiting list) during the study period
5. Diagnosis of peripartum or chemotherapy-induced cardiomyopathy or acute myocarditis in the previous 12 months
6. Implantation of a cardiac resynchronization therapy device in the previous 4 weeks before Screening
7. Restrictive, constrictive, hypertrophic, or obstructive cardiomyopathy
8. Untreated ventricular arrhythmia with syncope in the previous 4 weeks before Screening
9. History of, or current diagnosis of, a severe swallowing disorder, moderate-to-severe gastroparesis, or major GI surgery (e.g., bariatric surgery or large bowel resection)
10. A major CV event within 4 weeks prior to Screening, including acute myocardial infarction, stroke (or transient ischemic attack), a life-threatening atrial or ventricular arrhythmia, or resuscitated cardiac arrest
11. Note: This exclusion criterion is included in the new Inclusion Criterion 9
12. Liver enzymes (alanine aminotransferase, aspartate aminotransferase) >5 times upper limit of normal at Screening based on the local laboratory
13. Diagnosis or treatment of a malignancy in the past 2 years, excluding non-melanoma skin cancer and carcinoma in situ of the cervix, prostate cancer with Gleason score <7, or a condition highly likely to transform into a malignancy during the study
14. Presence of any condition (e.g., drug/alcohol abuse; acute illness), in the opinion of the Investigator, that places the subject at undue risk, or prevents complete participation in the trial procedures, or potentially jeopardizes the quality of the study data

15. Use of any investigational product for an unapproved indication within 4 weeks before Screening or currently enrolled in any other type of medical research judged not to be scientifically or medically compatible with this study
16. Known hypersensitivity to patiromer (RLY5016) or its components
17. Note: This exclusion criterion is modified and partially incorporated in the Exclusion Criterion 18
18. Subjects currently being treated with or having taken any one of the following medications in the 7 days prior to Screening: sodium or calcium polystyrene sulfonate or sodium zirconium cyclosilicate, or patiromer
19. An employee, spouse, or family member of the Sponsor (Vifor Pharma), investigational site or the CRO

5.4 Randomization Criteria

Subject may be randomized anytime (but no later than 12 weeks) during the Run-in Phase when they meet all of the following criteria:

1. Current MRA dose is at least the target dose* (e.g., spironolactone 50 mg/day, eplerenone 50 mg/day) and has been stable for at least 1 week.
2. Current ACEi/ARB/ARNi is $\geq 50\%$ of the target dose* and has been stable for at least 1 week.
3. Current patiromer dose is at least 1 packet daily.
4. Current local serum K^+ level is $\geq 4.0 - \leq 5.0$ mEq/L.

* Study-specific target doses as per Table 4 in the Study Manual.

5.5 Discontinuing Patiromer/Placebo or Withdrawal of Subjects

5.5.1 Discontinuation from Patiromer/Placebo

The management of ACEi/ARB/ARNi and/or MRA are at the discretion of the Investigator during the Blinded Treatment Phase. If one or more ACEi/ARB/ARNi and/or MRA are adjusted, patiromer/placebo may be adjusted accordingly, based on changes in local serum K^+ levels. The lowest dose of patiromer/placebo is 0 packets/day. It is recommended to discuss with the subject a study treatment interruption (dose level 0 packets/day) rather than a permanent patiromer/placebo discontinuation, which should only occur when it is requested by the Investigator or the subject.

Subjects who discontinue from patiromer/placebo treatment after randomization and prior to completion of the study will be encouraged to return within 2 weeks, or as soon as possible thereafter, for a Potassium Assessment Visit (see Section 8.6). Subjects who

discontinue from patiromer/placebo treatment after randomization and prior to the common EoS will continue in the study for collection of composite endpoint events. These subjects will be treated in accordance with the standard of care per the Investigator's judgment.

Note: Subjects who discontinue from patiromer during the Run-in Phase will also be encouraged to return for a Potassium Assessment Visit within 2 weeks, or as soon as possible thereafter.

5.5.2 Withdrawal from Study

5.5.2.1 Withdrawal of Consent

Within the provisions of informed consent and good clinical judgment with respect to the subject's safety, every attempt should be made to have subjects complete both the Treatment Phase and the Potassium Assessment Visit after discontinuation of patiromer/placebo. Subjects will be informed that they will be free to withdraw from the study at any time. However, should a subject withdraw, every effort will be made to determine the reason why the subject has withdrawn his/her consent. Although subjects will not be obliged to give a reason for withdrawing consent, the Investigator will use best efforts to obtain the reason, while fully respecting the subject's rights. Reasons for withdrawal of consent, when provided by the subject, will be recorded in the eCRF, and every effort should be made by the site to ensure that the subject completes the procedures described for early termination (ET) (Section 8.5). Every effort will be made to contact a subject who fails to attend a study visit, in order to ensure that the subject is in satisfactory health.

The subject who wishes to withdraw consent will be offered the opportunity to withdraw consent only partially and to accept any or all of the following:

- Providing information about his/her own health status by telephone or other means until the common EoS date
- Allowing Primary Care physicians or family to be contacted to provide information about the subject's health status
- Allowing 1 final contact at the end of the study (at or after the EoS)

5.5.2.2 Investigator-Withdrawn Subject

The Investigator and/or the Medical Monitor may exercise his or her medical judgment to terminate a subject's participation in the study if they determine that the subject's continued participation in the study is a potential safety concern, related to e.g., subject's non-adherence to the study protocol, subject's non-compliance to study medication, any medical condition that the Investigator or Sponsor determines may jeopardize the subject's safety if he or she continues in the study, subject's excessive drug/alcohol abuse. The Investigator may also terminate a subject's participation due to any condition preventing complete participation in the trial procedures, or potentially jeopardizing the quality of the study data. The Investigator will immediately inform the Medical Monitor of plans for early

withdrawal of a subject from the study. Investigator-withdrawn subjects will also be offered the opportunity to consent to the 3 options described above. All subjects withdrawn early from the study for any reason will complete the procedures described for ET (Section 8.5) and be followed for safety after receiving the last dose of study medications. Randomized subjects withdrawn from the study for any reason will not be replaced.

